#### **4.2.3 Exploratory Endpoints**

The exploratory endpoints for both Part A and B of this study are as follows:

- To assess plasma levels and PK parameters ( $C_{max}$ ,  $t_{max}$ ,  $C_{min}$ ,  $C_{last}$ ,  $t_{last}$ ,  $AUC_{0-8}$ ,  $AUC_{0-24}$ ,  $AUC_{0-\infty}$ ,  $t_{1/2}$  and AR) of metabolite(s) when feasible.
- To evaluate the relationship between CB-103 plasma concentrations and/or PK parameters (e.g.,  $C_{max}$  and  $AUC_{0-24}$ ) and safety, efficacy and PD parameters.
- To assess NOTCH, NOTCH-related genes, and NOTCH target genes expression changes in pre- and post-treatment tumour tissue samples, whole blood / plasma samples and hair follicles in solid tumours and in T-lymphocytes from blood and/or bone marrow samples, whole blood and plasma in T-ALL/T-LBL, and assess their relation to clinical activity of CB-103.
- To assess the cerebrospinal fluid (CSF) exposure of CB-103 in haematological malignancies, in patients in whom IT prophylaxis is planned by the treating physician.
- To assess certain genotypes (e.g. cytochrome P450 enzymes or NAT) and assess relation to PK outcome data.
- To assess NOTCH1-4 NICD expression assessed by IHC staining or by Western Blot in pre- and post-treatment in solid tumour tissue samples and to assess their relation to clinical activity of CB-103.
- To assess NOTCH mutations by genomic mutation analysis in tumour tissue samples in solid tumours and in T-lymphocytes from blood and/or bone marrow samples, whole blood and plasma in T-ALL/T-LBL, and to assess their relation to clinical activity of CB-103 treatment.
- To assess the changes in the percentage of mutated alleles in liquid biopsies pre- and post CB-103 dosing and their relation to the effect of CB-103 treatment.
- To evaluate the intra-tumoral quantification of CB-103 in solid tumour tissue samples.
- To profile tumour tissue samples in solid tumours and T-lymphocytes from blood and/or bone marrow samples in T-ALL/T-LBL by single cell RNA-seq and/or other gene expression and genetic profiling techniques.
- To explore and assess changes in the immune system in pre- and post-CB-103 dosing whole blood and plasma (e.g., measure expression of cytokines/chemokines by RNA expression analysis, quantify pro-inflammatory and anti-inflammatory cytokines and chemokines, phenotype different types of immune cells (T cells, B cells, dendritic cells and macrophages, etc.) using flow cytometry).
- To assess change from baseline cardiac intervals versus increasing plasma CB-103 concentrations.

- To assess the metabolic profile of CB-103 in biological matrices such as urine and/or stool samples based on metabolic expressions of CB-103 in urine and/or stool samples

## **5. STUDY DESIGN**

### **5.1 DESCRIPTION OF STUDY**

#### **5.1.1 Overview of Study Design**

This study is designed as an open-label, non-randomised, uncontrolled Phase I/IIA dose escalation study with expansion cohorts of CB-103 administered orally on a once-daily schedule, based on a 28-day treatment cycle. The administration schedule may be adapted during dose escalation (e.g. twice-daily, intermittent dosing schedule) depending on the PK and safety signals that occur.

There will be two parts to this study. The aim of the Phase I part of the study (Part A) with the dose escalation followed by an MTD/RP2D confirmatory cohort is to determine the MTD/RP2D. An adaptive 2-parameter BLRM for EWOC will be used in Part A to guide determination of the MTD or the RP2D.

Part A will be followed by the expansion Phase IIA (Part B of the study) to determine preliminary evidence of anti-tumour activity and to confirm the safety of the CB-103 MTD/RP2D in different expansion arms consisting of patients stratified into various pre-selected cancer indications at an advanced or metastatic stage of the disease.

#### **Part A – Dose escalation (Phase I)**

Part A will be a dose-finding study based on a 2-parameter BLRM to investigate the safety and tolerability of sequentially enrolled dose cohorts of at least 3, up to 6 patients per dose cohort. Depending on the BLRM, additional patients may be enrolled in some dose cohorts. The first two patients of each dose level will be enrolled in a staggered approach with at least 1 day apart between first dosing of these patients. Subsequent patients may be enrolled concurrently, with at least 1 day apart from the second patient, whereby a dose cohort must be completed with regards to the DLT assessment period and be reviewed by the Cohort Review Committee (CRC) established for this study before further patients are dosed in the next dose cohort. The BLRM will be assessed for those patients satisfying the requirements for inclusion in the dose-determining set (DDS). After completion of a given dose cohort, or at any time the BLRM is updated, the decision to dose escalate and the actual dose and schedule chosen will depend on the recommendation of the BLRM about the highest admissible dose according to the EWOC principle and medical review of available clinical, pharmacokinetic and laboratory data. The outcome of these analyses and the respective datasets will be reviewed by the CRC consisting of the Investigators, Sponsor and CRO representatives, and independent functional experts as required (see Section 5.1.4.1). The CRC will make the decision to determine the next dose level and schedule for the next dose cohort.

Any dose level cohort that has been declared safe after the DLT period, may be expanded by individual patients in order to collect additional pharmacodynamic (PD) and pharmacokinetic (PK) information to support and/or confirm the mechanism of action and

explore doses at the currently tolerated dose level or below. These patients will be counted for the respective cohort at the future CRC meetings and will contribute towards the overall safety, PK, PD and clinical efficacy evaluation.

When the MTD/RP2D is defined, based on the decision of the CRC, approximately 45 additional NOTCH-positive patients with recurrent/metastatic ACC, breast cancer, r/r T-ALL/T-LBL, or any other solid tumour with proven Notch pathway activation will receive the MTD/RP2D dose to ascertain that optimal safety related to efficacy and pharmacodynamics in the tumour and in peripheral blood are achieved.

[figure not shown]
### **Part B - Expansion (Phase IIA)**

Part B will be the expansion phase following the determination of MTD/RP2D in Part A. Patients will be enrolled into one or several expansion arms. These arms will consist of patients with pre-selected cancer indications with tumour cells characterised by NOTCH over-activation to confirm safety of the MTD/RP2D of CB-103 and to explore its anti-tumour activity in each of the pre-selected indications. For the expansion arms a Bayesian hierarchical design will be applied for the preliminary efficacy analyses.

Enrolment into Part B of the study will start once the MTD or RP2D in Part A has been determined.

The study design is depicted in [Figure 4](#).

**Figure 4** Overview of study design

[figure not shown]
Abbreviations: ACC, adenoid cystic carcinoma; DG, dose group; MTD, maximum tolerated dose; pts, patients; ER, estrogen receptor; CRC, colorectal cancer; HCC, hepatocellular carcinoma; HER2, human epidermal growth factor receptor 2; PR, progesterone receptor; r/r, relapsed/refractory; RP2D, recommended phase 2 dose; TNBC, triple negative breast cancer.

### 5.1.1.1 Study Periods

The study is split into three periods in Part A and into 4 periods in Part B (Figure 5):

- Pre-screening period (Part A MTD/RP2D confirmatory cohort & Part B)
- Screening period (including baseline assessments)
- Treatment period (including an End-of-Treatment [EOT] visit)
- Safety follow-up period

**Figure 5** Study periods

### **Pre-screening period (Part A MTD/RP2D confirmatory cohort & Part B), for patients whose Notch pathway activation status is not known**

The pre-screening period starts once the patient has signed the “pre-screening” informed consent form (ICF) and ends once the patient has signed the “study” ICF.

In Part A (MTD/RP2D confirmatory cohort) & Part B, if the Notch status of the cancer has not been ascertained previously, investigational sites will need to pre-screen patients for either NOTCH pathway activating mutations, amplifications/translocations or gene/protein expression alterations. The investigational site must obtain the signature of the patient on the pre-screening consent form. If there is no archived tumour sample available or if available, but older than 6 months, then a fresh tumour biopsy has to be obtained. The patient’s tumour samples can be sent for characterisation of NOTCH pathway-activation to the central laboratory if the analysis cannot be done locally. The result of the analysis will be communicated within approximately 7 working days to the respective investigational site.

### **Screening period**

The 28-day screening period includes the baseline and starts once a patient has provided written informed consent to participate in the study; it ends on the day prior to the planned 1st administration of CB-103 (day -28 to day -1).

Because of the low overall incidence of cancers with an activated NOTCH signalling pathway (Ntziachristos et al., 2014), enrolment of patients in Part A (dose-escalation) will not include mandatory screening for NOTCH pathway over-activation in tumour tissue.

However, in line with the site's standard-of-care, the investigational sites are encouraged to evaluate their patients prior to study entry with regard to the NOTCH activation level in tumours (either mutations, amplifications/translocations or gene/protein expression alterations) and to consider enrolling patients preferably with a signal of NOTCH over-activation. The selection of patients for Part A (dose-escalation) may be done in favour of those who show evidence of over-activation and genetic aberrations of the NOTCH signalling pathway.

Patients enrolling in the Part A MTD/RP2D confirmatory cohort and in Part B (dose expansion) have to have tumours with demonstrated NOTCH pathway activation. NOTCH status will be determined as outlined in the Inclusion Criteria by using established methods.

### **Baseline period**

Baseline assessments are performed from three days prior to, until the day prior to the planned 1st administration of CB-103 (day -3 to day -1).

### **Treatment period**

Solid tumours (six-twelve cycles): the treatment period commences on the first day of the first cycle of CB-103 treatment (1st administration of CB-103) and ends on the last day of dosing (within the 6 cycles period for Part A or 12 cycles period for Part B).

T-ALL/T-LBL: initial treatment with CB-103 single agent is given for 28 days (one cycle). Patients are assessed for disease response on day 29 ( $\pm 3$  days); however, if the day 29 marrow is hypocellular (cellularity  $\leq 15\%$ ), then treatment with CB-103 may continue and a repeat bone marrow biopsy is obtained one week later (day 36) to assess response.

Patients achieving a CR are eligible to receive 2 additional courses of CB-103 as consolidation therapy at the same dose and schedule as outlined above. Treatment may be discontinued if the patient is scheduled for HCT, otherwise additional courses of CB-103 until relapse may be given after discussion with the Sponsor.

If residual leukaemia/lymphoma is documented at the point of marrow recovery (cellularity  $\geq 15\%$ ) after the first induction cycle, then a second course of CB-103 is administered.

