## 4.2 STUDY ENDPOINTS

### 4.2.1 Primary Endpoints

The primary endpoint for Phase I, Part A (dose-escalation) of this study is as follows:

- The number of patients experiencing dose-limiting toxicity (DLT) during the first 28-day cycle of CB-103 treatment

The primary endpoint for Phase I, Part A (confirmatory) of this study is as follows:

- The incidence rate, severity and relationship to CB-103 of adverse drug reactions and serious drug reactions according to common terminology criteria for adverse events (CTCAE) V4.03, safety laboratory, vital signs, ECG and ECHO/MUGA assessments.

The primary endpoint for Phase IIA, Part B of this study is as follows:

- To assess tumour response rates in each expansion arm as best overall response rate (in solid tumours complete response [CR] + partial response [PR]) assessed by Response Evaluation Criteria in Solid Tumours (RECIST 1.1); in T-ALL/T-LBL patients, confirmed CR and Complete Remission with Incomplete Hematologic Recovery (CRi) assessed by the criteria according to NCCN Guidelines on Adult Acute Lymphoblastic Leukaemia (Version 1.2020).

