### **Safety follow-up period**

All patients will have a safety follow-up for adverse events and serious adverse events 28 days after the last dose of CB-103 after which the end-of-study is reached. The safety follow-up visit must be performed by all patients who have received at least one administration of CB-103. All adverse events and/or serious adverse events occurring

during this period will be recorded in the Adverse Event electronic Case Report Form (eCRF).

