### 10.5.2 Part B (Expansion)

Once the MTD/RP2D is determined, enrolment into Part B (expansion) can be started by enrolling patients into several expansion arms for selected cancer indications. All patients in Part B will need to have tumours characterised by alterations and over-activation of the NOTCH signalling pathway (mutations, translocations, over-expressions).

For the primary analysis of the expansion arms a Bayesian hierarchical exchangeable binomial design will be used. The assumption of the model is that the true response rate in each of the preliminary indications for the Part B expansion arms is fully exchangeable.

For these indications the response criteria for success is a point estimate (from the model) above 25%.

The T-ALL/T-LBL indications are assumed to be only partially exchangeable with other indications. The success criteria for this indication is a point estimate (from the model) above 40%.

A robust hierarchical model (Neuenschwander et al., 2015) will be used for the analysis of the response rate  $p_k$  in the different indications  $k = 1, \dots, K$ . The number of responders in each indication follows a binomial likelihood function. For exchangeable indications ( $k = 1, \dots, K - 1$ ) it is assumed that

$$\text{logit}(p_k) \sim N(\mu, \tau^2)$$

On the other hand, for the partially (or non-) exchangeable indication  $K$  we use the mixture

$$\text{logit}(p_K) \sim N(\mu, \tau^2) \text{ with probability } \pi,$$

$$\text{logit}(p_K) \sim N(m, s^2) \text{ with probability } 1 - \pi$$

setting  $m = \text{logit}(0.3)$  and  $s = 2.2$ .

Further, the following weakly informative priors (Friede et al., 2016; Friede et al., 2017) are used:

$$\mu \sim N(\text{logit}(0.2), 2.5^2)$$

$$\tau \sim HN(1)$$

For these exchangeable indications, the advantage of this model is the fact that borrowing information across indications improves the precision of the estimators of the response rate. On the other hand, for the possibly different indication, the mixture approach hedges for a too-optimistic assumption about similarity. Therefore, the described approach captures the design adequately.

Other characterisations of the posterior distribution will be evaluated as appropriate. The final analysis will take place after the last expansion arm was closed for futility or the last patient of the last expansion arm had the final end-of-study visit.

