-  Bone marrow biopsy and/or aspirate (T-ALL/T-LBL): a bone marrow biopsy and/or aspirate will be obtained to assess bone marrow cellularity and to determine the percentage of leukemic blasts, including assessment of minimal residual disease (MRD) to confirm remission status. At the baseline assessment by bone marrow biopsy and/or aspirate is within 2 weeks and no less than 1 day before the first dose of CB-103. Then Patients are assessed for disease response by Bone marrow biopsy and/or aspirate on day 29, if the blasts in bone marrow  $<5\%$  but marrow is hypocellular (cellularity  $\leq 15\%$ ) on day 29 ( $\pm 3$  days), then a repeat bone marrow biopsy and/or aspirate is obtained 1 week later to assess response; if residual leukaemia is present, repeated bone marrow biopsy and/or aspirate will be obtained per 28 days until to CR or Cri. A response (CR or Cri) must be confirmed no less than 28 days from the first evidence of response by bone marrow core biopsy as indicated. In case of CR or Cri confirmed by bone marrow biopsy and/or aspirate on 2 bone marrow biopsy and/or aspirate assessments no less than 28 days apart the interval between assessments, bone marrow biopsy and/or aspirate assessment may be increased to every 8 weeks until to PD or EOS (whichever is earlier).
-  Lumbar puncture (T-ALL/T-LBL) for prophylactic intrathecal therapy: if prophylactic intrathecal therapy is foreseen by the treating physician, a lumbar puncture may be performed up to 3 days before the first dose of CB-103, and, depending on the response of the patient, may be repeated at the discretion of the treating physician at the end of the first cycle of treatment with CB-103, and at the end of any subsequent cycle of treatment with CB-103, if more than one is warranted.
-  CSF sample (T-ALL/T-LBL): In patients in whom a lumbar puncture is done (e.g., for intrathecal prophylaxis) a CSF sample should be taken on or around cycle 1 day 28, if clinically feasible, to determine the exposure of CB-103 in the CSF.

CONFIDENTIAL

May not be used, divulged, published, or otherwise disclosed without the consent of Cellestia Biotech AG

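### T-ALL/T-LBL responders who stop CB-103 without relapse have no scheduled relapse follow-up after EOS, and neither document has a transplant rule for DOR or PFS

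*Protocol*

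**What the plan says.** Protocol 5.1.1.1 (Treatment period) gives one 28-day cycle, a response marrow on day 29 (±3 days), and then: "Patients achieving a CR are eligible to receive 2 additional courses of CB-103 as consolidation therapy". It continues: "Treatment may be discontinued if the patient is scheduled for HCT". For patients not going to transplant, the same sentence leaves the matter open: "otherwise additional courses of CB-103 until relapse may be given after discussion with the Sponsor". A responder can therefore come off drug without relapse, either for HCT or because the two courses are finished and no more are agreed.

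Under the safety follow-up heading of the same section, patients are seen "28 days after the last dose of CB-103 after which the end-of-study is reached". Marrow monitoring stops there too. For confirmed responders, Appendix 2 footnote 21 says "bone marrow biopsy and/or aspirate assessment may be increased to every 8 weeks until to PD or EOS (whichever is earlier"; Appendix 1 footnote 24 has the same rule. After EOS, section 8.1 and the schedules provide survival contacts only: three-monthly for one year and, in Part B, six-monthly in the second year.

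On the endpoints:
- The Part B primary endpoint is, "in T-ALL/T-LBL patients, confirmed CR and Complete Remission with Incomplete Hematologic Recovery (CRi" (4.2.1). Footnote 21 adds: "A response (CR or Cri) must be confirmed no less than 28 days from the first evidence of response". Section 10.5.2 sets the bar: "The success criteria for this indication is a point estimate (from the model) above 40" per cent.
- Protocol 10.6.2 runs DOR to first PD or relapse. SAP 5.6.2.3 and 5.6.2.5 run DOR and PFS to progression or death from any cause and otherwise censor at the last evaluable tumour assessment (for DOR, alternatively at the last follow-up for PD).
- No analysis text in either document mentions HCT.

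**The concern.** Loss of relapse information here is built into the schedule. A responder who stops as the protocol allows leaves disease assessment while still in remission, and the remaining contacts ask only about survival. Under the SAP definitions the two components of the endpoint are then treated unequally. A death after EOS, for example after transplant, can enter as an event, whereas a relapse in the same month goes unrecorded. If the relapsed patient later dies, the event is dated at death and the time in relapse counts as response or progression-free time. If the patient does not die, follow-up is censored at the last assessment before EOS. SAP 5.1 also moves data from long-term survival follow-up to a separate combined analysis, so the same patient may be censored in one report and have an event in the other.

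Transplant makes this harder to interpret. It is itself an anti-leukaemic treatment, and without a stated rule DOR and PFS can be computed with or without the post-transplant period after the data have been seen.

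A second, narrower question concerns confirmation. If a patient leaves for HCT very early, the confirmatory marrow may fall due only after EOS, and nothing says whether it would still count.

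**Working it through.** **Convention.** Day 1 is the first dose and cycles are 28 days. Check: C3D1 = 2 × 28 + 1 = day 57, as printed in the Appendix 1 schedule.

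**Formulas.** EOS = last-dose day + 28. Earliest confirmation = day of first CR + 28. Longest observable DOR = EOS − day of first CR + 1 (SAP 5.1 duration rule).

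| Course | Last dose | EOS | Earliest confirmation | Longest observable DOR |
|---|---|---|---|---|
| CR day 29, stop at once | 28 | 56 | 57 | 28 days, if confirmed at all |
| CR day 29, one consolidation course | 56 | 84 | 57 | 84 − 29 + 1 = 56 days |
| CR day 29, two courses | 84 | 112 | 57 | 112 − 29 + 1 = 84 days |
| CR first on day 57, stop at once | 56 | 84 | 85 | 28 days, if confirmed at all |
| CR first on day 57, two further courses | 112 | 140 | 85 | 140 − 57 + 1 = 84 days |

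**Relapse capture.** For anyone who stops after no more than two consolidation courses, 84 days is the ceiling. It may not be reached: if marrows move to 8-weekly after a day-57 confirmation, the next is due on day 57 + 56 = 113, one day after EOS (a ±3-day window would allow day 110). EOS on day 112 is 112 / 30.4375 = 3.7 months, while 10.6.2 plans T-ALL/T-LBL rates out to Month 9. For patients who stopped by plan, nothing is scheduled to supply the Month 5, 7 and 9 values.

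**Share of relapses inside the ceiling.** Assume exponential DOR with median m days; the documents give no median. Share = 1 − 0.5^(84/m).
- m = 3 months (91.3 days): 47% inside, 53% after.
- m = 6 months (182.6 days): 27% inside, 73% after.
- m = 12 months (365.3 days): 15% inside, 85% after.

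**Confirmation.** With the first marrow on day 26 to 32, earliest confirmation is day 54 to 60 against EOS on day 56. That is between 2 days before and 4 days after EOS, nominally 1 day after. With one or two consolidation courses, day 57 comes 84 − 57 = 27 or 112 − 57 = 55 days before EOS, so there is no clash.

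**Effect of one unconfirmed CR.** It moves the raw rate by 1/20 = 5 points or 1/10 = 10 points. For example, 9/20 = 45% becomes 8/20 = 40%. The criterion itself uses the model estimate, so this is only indicative.

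**The case against.** The strongest reply is that many responders will not be affected. Section 7.4 treats until progression, and 5.1.1.1 allows further courses until relapse; those patients keep having marrows. This stands, and it limits the point to patients who stop.

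The plan also has some assessment off drug. SAP 5.6.2 lists a tumour assessment at EOT, the schedules mark an efficacy (PFS) assessment there, and unscheduled marrows are possible. Protocol 5.1.3 speaks of patients followed for progression, and SAP 5.6.2.3 of a last follow-up for PD. But EOT is within 14 days of the last dose, before EOS, and no schedule supplies the later progression follow-up that these sentences presuppose.

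On confirmation, a reader might infer that any patient going to HCT loses the chance to be confirmed. The documents do not support that. The HCT sentence can be read as a choice made after consolidation, and then confirmation comes well before EOS. Even for an immediate stop, the one-day miss depends on nominal dates within a ±3-day window.

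A reader might also infer that the plan leaves an unconfirmed CR uncounted. It does not: confirmed CR/CRi over all treated T-ALL/T-LBL patients (protocol Efficacy Analyses) makes that patient a non-responder. Two texts are looser: an ORR sentence in the synopsis without the word confirmed, and Appendix 8, which asks only for four weeks without recurrence.

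Finally, the SAP covers Part A only. Its event definitions apply to T-ALL/T-LBL patients in the confirmatory cohort; for Part B only the protocol text is available. Protocol 10.6.2 does not name death in DOR, so the unequal treatment of death and relapse is explicit for Part A only. The absence of relapse follow-up applies to both parts.

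**Conclusion.** The point holds for the secondary endpoints. For a T-ALL/T-LBL responder who stops without relapse, relapse after EOS is not captured, observed DOR is capped at 84 days after two consolidation courses (less after fewer), and HCT handling is undefined in both documents. How many relapses this misses depends on the assumed median: 53% to 85% for medians of 3 to 12 months, among patients who stop by plan. The proportion who stop is not given and is not estimated here.

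For the primary endpoint the point is small and conditional. EOS and the earliest confirmation day nearly coincide only when dosing ends with the course that first shows CR. It is tempting to turn this into a large loss of power against the 40% criterion. That would need an assumed share of responders leaving in that narrow window, an assumed true response rate and no borrowing between arms; the documents give neither share nor rate, and the model may borrow. What can be said is that each such patient costs 5 to 10 points of raw response rate in an arm of 20 to 10.

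The change is worth making because it is cheap and because relapse dates not asked for at the time are hard to recover later.

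**What to change.** (a) Add relapse or progression status with date, and date of HCT, to the survival contacts already planned (8.1; Appendix 1 footnote 17; Appendix 2 footnote 15). Use these dates for DOR and PFS in T-ALL/T-LBL.

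(b) In protocol 10.6.2 and SAP 5.6.2.3 and 5.6.2.5, state that DOR and PFS are reported without censoring at HCT, with censoring at HCT as a sensitivity analysis.

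(c) State that the confirmatory marrow already required at 28 days or more counts even if it falls after the patient's EOS, provided no conditioning or new anti-leukaemic therapy has started. Report how many CR/CRi patients went to HCT unconfirmed, and add a sensitivity analysis counting them as responders. The primary definition of response stays as it is.

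No extra marrow before conditioning and no continued marrows off drug are proposed: these are added procedures for patients, and the gap can be narrowed without them. The cost is one or two eCRF items and a little more analysis, with no new visits or patients. The drawback is that relapse dates obtained at three-monthly contacts are less exact than dates from scheduled marrows.
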